## 2.2.2 Other Exploratory Endpoints

- To evaluate the relationship between physical activity (type and intensity) and bleedings
- To evaluate the sleep duration and sleep stage in participant patients.
- Sleep duration (overall) and sleep stage duration (Wake, REM, Light, Deep) collected through a wearable device (i.e., fitness tracker). Sleep duration (overall and by stage) will be analyzed for the valid days of monitoring (i.e., defined as at least 10 wearing hours per day).
- To observe patients, on primary and secondary objectives, for additional 6 months if new therapies become commercially available for patients with Haemophilia A without inhibitors against FVIII, during the course of the study and if patient will start such treatments during the observation period
- Physical examination at baseline and every three months.
- Vital signs at baseline and every three months.

## 2.3 DETERMINATION OF SAMPLE SIZE

Given the exploratory nature and the objectives of this non-interventional study, rather than testing a formal hypothesis, a justification based on epidemiologic data from the Italian registry of congenital bleeding disorders (Giampaolo et al. 2017) was considered more appropriate than a power calculation in the traditional fashion or using an estimation approach through the precision of confidence intervals.

The total sample size planned is approximately 150 patients overall, 125 patients with severe Haemophilia A and 25 patients with moderate Haemophilia A.

Based on data collected from the 54 Haemophilia Treatment Centers, members of the Italian Association of Haemophilia Centres (AICE), it is estimated that this planned number

of participants will represent approximately 10-15% of patients with Haemophilia A in Italy, in the same age range and category of severity planned for this study.

The estimated sample size (150 subjects) allows to obtain 95% confidence intervals with half-width (i.e., precision) less than or equal to 17% of the standard deviation with a probability of over 80%.

### **2.3.1      Change in sample size.**

The enrolment was interrupted on 30 April 2021 due to difficulties associated with the SARS-COV-2 pandemic that limited the participation of potential patients in the study within the acceptable enrolment period.. Of the anticipated 150 patients, 107 (71.3%) were included in the study. The reduction of the sample size to 107 patients involves a slight reduction in precision, i.e., an increase in the half-width that will be observed to be less than or equal to 20% (instead of 17% reported in the original protocol) of the standard deviation with an 80% probability. Hence, the reduction of the sample size due to the early interruption of the enrolment does not cause a significant deviation from the planned precision of the estimates.

### **2.4            ANALYSIS TIMING**

One interim analysis is planned, when all enrolled patients have completed 6 months of observation, to have a preliminary evaluation of results.

Due to the observational nature of this study, no adjustments will be done for the derivation of the p-values of the proposed statistical tests.

The final analysis will be done the last enrolled subject will have finished the planned observational period of 12 months, or in case of starting a new therapy, when all applicable patients have completed the 6 months of observation after the first new therapy administration. See Table 1 for further details.

## **3.            STUDY CONDUCT**

### **3.1            RANDOMIZATION**

NA

### **3.2            INDEPENDENT REVIEW FACILITY**

NA

### **3.3            DATA MONITORING**

NA

### **3.4 DATA REVIEW MEETING**

Once the study database is considered clean and before database lock, a data review meeting will be performed. During this meeting the study data will be reviewed to identify potential issues and document decisions taken to address them before the database is locked and the analysis of the data starts.

## **4. STATISTICAL METHODS**

Appropriate descriptive statistics will be produced, according to the variable. For continuous data n, mean, standard deviation (SD), median, I and III quartile, and range (minimum and maximum) will be presented. For categorical data, frequency distributions and percentages will be presented.

Unless otherwise specified, hypothesis testing (exploratory in nature) will be carried out at the alpha = 0.050 level (two-sided). For all inferential analyses, the p-values will be rounded to three decimal places. Due to the exploratory nature of this study, no adjustment for multiplicity will be made.

Any unplanned analyses as well as deviations from the original SAP will be clearly documented in the Clinical Study Report.

All the data collected and derived in the study will be presented in subject data listings.

With reference to the ePROs and physical activity data (i.e. all data derived from ePRO app and the fitness tracker), only data collected between the informed consent date and Date of patient completion or withdrawal (extremes included) will be analyzed. For the interim analysis, the minimum between Date of patient completion or withdrawal and the cut-off date will be considered as upper bound.

### **4.1 ANALYSIS POPULATIONS**

#### **4.1.1 Enrolled Population (ENR)**

The Enrolled Population will consist of all patients for whom the inclusion/exclusion criteria have been verified and met.

#### **4.1.2 Evaluable population**

The evaluable population will consist of all enrolled patients with at least 6 valid months of physical activity evaluations during the study.

The patients with 6 valid months of physical activity will be defined by the presence of the two following conditions:

- an Extent of Exposure to the fitness tracker of at least 6 months (180 days) (see Section 4.3.1 for the definition of Exposure).

AND

- a compliance to the use of the fitness tracker of at least 50% in the period defined by the extent of exposure (see Section 4.3.2.1 for the definition of the compliance respect to the exposure).

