6.7 STATISTICAL CONSIDERATIONS

The appointed CRO will be responsible for the statistical analysis of the study. All statistical analyses and data processing will be performed using Statistical Analysis Software (SAS), release 9.4 or later, under Windows 7 or Windows 10 Pro operating system.

The statistical methods planned in this study protocol (see below) will be detailed, agreed and approved in a statistical analysis plan (SAP) which will be finalised before database lock.

Descriptive statistics will be provided in summary tables according to the type of the variable. Continuous variables will be summarized by using number of cases, mean, and standard deviation, median, quartiles and range (*i.e.*, minimum and maximum). Categorical variables will be summarized by using frequency and percent distribution.

Populations for analysis

The following populations will be considered for the analysis:

- Enrolled population: all patients for whom the inclusion/exclusion criteria have been verified and met;
- Evaluable population: all enrolled patients with at least 6 valid months of physical activity evaluations during monitoring through the fitness tracker during the study.

Analysis of demographic an disease characteristics will be performed in the Enrolled population. Analysis of primary, secondary and exploratory variables will be performed in the Evaluable population.

Missing data

Imputation methods for missing values will be discussed and detailed in the SAP as deemed appropriate.

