### **Amendment 1.2: 08 June 2022:**

The changes done in this amendment mainly regard the definition of the evaluable population. The following section have been changed:

- Section 4.1.2: the definition of the Evaluable population has been updated by including a condition on the compliance to the use of the fitness tracker in addition to the presence of a valid period defined by an exposure of at least 180 days (6 months)
- Section 4.3.2.1: a definition of the compliance to the use of fitness tracker relatively to the period defined by the extent of exposure (from the first valid day to the last valid day, extremes included) has been added.

Moreover, the following sentence has been added in Section 4.0:

*With reference to the ePROs and physical activity data (i.e. all data derived from ePRO app and the fitness tracker), only data collected between the informed consent date and Date of patient completion or withdrawal (extremes included) will be analyzed. For the interim analysis, the minimum between Date of patient completion or withdrawal and the cut-off date will be considered as upper bound.*

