## 4.3 EVALUATION OF COMPLIANCE AND EXPOSURE

### 4.3.1 Exposure to use of the fitness tracker

On a per patient basis, the evaluation of the exposure to the use of the fitness tracker will be done using the following formula:

$$\text{Exposure (days)} = \text{date of the last valid day} - \text{date of first valid day} + 1$$

where a “valid day” is defined as a day in which the fitness tracker is worn for at least 10 hours. The wearing time derivation is presented in the Appendix 3.

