##### **4.3.2.1 Compliance to use of the fitness tracker (respect to the exposure)**

On a per patient basis, the evaluation of the compliance during the period defined by the exposure will be done using the following formula:

$$\text{Compliance (\%)} = \frac{\text{total number of valid days}}{\text{between the first and last valid days}} \times 100$$

where a “valid day” is defined as a day in which the fitness tracker is worn for at least 10 hours. The wearing time derivation is presented in the Appendix 3.

This definition of compliance will be used to define the Evaluable population.

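### The Evaluable rule takes 50% wear over each patient's own first-to-last-valid-day span, so one later isolated valid day can remove a patient who already qualifies

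*SAP*

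**What the plan says.** Protocol 6.7 defines the Evaluable population as "all enrolled patients with at least 6 valid months of physical activity evaluations" and leaves it there. SAP 4.1.2 repeats the phrase and makes it operational: such patients "will be defined by the presence of the two following conditions", joined by AND.

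- **Span.** Exposure must reach 180 days, which the SAP equates with 6 months. SAP 4.3.1 computes exposure as the "date of the last valid day" minus the date of the first, plus 1. It is a calendar span, not a count of valid days.
- **Density.** The patient must show "a compliance to the use of the fitness tracker of at least 50% in the period defined by the extent of exposure". The SAP's note on Amendment 1.2 gives that period as running "from the first valid day to the last valid day, extremes included". SAP 4.3.2 also has a whole-study compliance, but SAP 4.3.2.1 says of the within-span version: "This definition of compliance will be used to define the Evaluable population".

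A valid day "is defined as a day in which the fitness tracker is worn for at least 10 hours". No minimum number of valid days is stated. SAP 4.1.3 has all objectives analysed on both the Evaluable and the ITT populations; the ITT set has no wear requirement.

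**The concern.** The first and last valid days set the denominator of the density condition, so each patient's own wear pattern decides how many valid days that patient must supply. An isolated valid day after a gap adds 1 to the numerator and the whole gap to the denominator. More valid data can therefore turn a qualifying patient into a non-qualifying one, which a rule meant to certify sufficient data should not do.

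Three consequences follow.

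- The co-primary endpoints in SAP 4.4.1 are each patient's median over all valid days. The count of valid days supports that median, yet the rule can accept 90 and refuse 182. The label of six valid months does not describe such a set.
- A patient who is Evaluable at the interim analysis can cease to be so at the final analysis after contributing more data.
- Patients who start a newly approved drug between Month 6 and Month 12 may be observed for up to 18 months. If they keep wearing the tracker, the number of valid days they need rises accordingly.

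**Working it through.** **Inputs.** Span threshold 180 days, density threshold 50%, both required (SAP 4.1.2). Span S = last valid day − first valid day + 1 (SAP 4.3.1). Standard observation 12 months, about 365 days; maximum 18 months (SAP 2, Table 1). Month length 30.4375 days (SAP 4.4.2, HRQoL and pain). Below, day 1 is the patient's first valid day and V is the number of valid days.

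**The plan's own figure.** 6 × 30 = 180 days, as stated. With the SAP's month length, 6 × 30.4375 = 182.6 days, within 3%. The 180 is not in dispute.

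**Rule.** Evaluable if S ≥ 180 and V/S ≥ 0.50. The smallest qualifying V is S/2, rounded up.

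| Span S (days) | Valid days needed | Largest V that fails on density |
|---|---|---|
| 180 | 90 | 89 |
| 365 | 183 | 182 (182/365 = 49.9%) |
| 548 (18 × 30.4375) | 274 | 273 (273/548 = 49.8%) |

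**Boundary comparison.** The smallest record admitted is 90 in 180. At a 365-day span the largest record refused is 182, and 182/90 = 2.02. At 548 days it is 273, and 273/90 = 3.03.

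**One more valid day.** A patient with V valid days in a 180-day span is removed by a single later valid day on day D when (V + 1)/D < 0.50, that is D > 2(V + 1). The first such day is 2(V + 1) + 1.

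| Valid days in the first 180 | First day on which one more valid day disqualifies |
|---|---|
| 90 (50%) | 183 (91/183 = 49.7%) |
| 108 (60%) | 219 |
| 144 (80%) | 291 |
| 170 (94%) | 343 (171/343 = 49.9%) |
| 180 (100%) | 363 |

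For the patient with 170, a single valid day on day 365 gives 171/365 = 46.8%.

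**Sensitivity to the denominator.** The fraction in SAP 4.3.2.1 is not fully legible in the available text. Amendment 1.2 supports the inclusive span S used here. With S − 1 or S − 2 instead, the largest record refused at 365 days is 181 and the smallest admitted is 90 or 89. The ratio is then 181/90 = 2.01 or 181/89 = 2.03, so the finding does not hang on this reading.

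**The case against.** A wear-density criterion is a legitimate choice, and 182 in 365 failing is simply what a 50% threshold means. Amendment 1.2 added the condition deliberately. The striking example also needs a long gap: the 170-in-180 patient is lost only after days 181 to 342, 162 days, pass without a valid day. The parallel ITT analysis retains every dropped patient who received the app and tracker. Whole-study compliance is summarised (SAP 4.3.2), and listings cover all enrolled patients with an evaluable flag (SAP Appendix 4).

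Much of this stands. Density should be kept, and the ITT run narrows the impact considerably. It does not cover everything: in SAP 4.4.1 and 4.4.2 the COVID-period and by-month summaries of daily activity, activity by type and WHO adherence are specified on the Evaluable set. Nor does a density criterion require this defect. The loss of a qualifying patient through extra data comes from stretching the denominator to the last valid day, and patients near 50% need only a short gap.

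A reader might infer more than the documents support:

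- **That everyone followed for 365 days with 90 to 182 valid days is lost.** The rule uses wear span, not follow-up. A patient with 90 valid days in the first 180 and none afterwards is included, however long the follow-up.
- **That selection depends only on when a patient stopped.** Every included patient has a span of at least 180 days and at least 90 valid days, so amount matters as well as timing.
- **That the Evaluable results are biased in a known direction.** The documents give no wear-time distribution. Neither the number of patients affected nor the direction of any effect can be stated, and the number could be zero.

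**Conclusion.** The point holds as a defect of the stated rule. The required number of valid days varies from 90 to 183 across spans within 12 months, and up to 274 at 18 months. A qualifying patient can be disqualified by further valid wear. At a wear span of 365 days, 90 to 182 valid days fail, while 90 in 180 pass and are described as six valid months.

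These figures follow from the SAP's definitions with the span counted inclusively, taking 12 and 18 months as 365 and 548 days. They describe what the rule can do, not how often it will. The practical reach is limited by the ITT analyses and is greatest for the summaries specified only on the Evaluable set. The change is cheap and worth making before database lock.

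**What to change.** In SAP 4.1.2 define Evaluable as having at least one period of 180 days or more, beginning and ending on a valid day, in which at least 50% of days are valid. Align SAP 4.3.2.1, which now ties the population to compliance over the full span. The endpoint summaries can still use all valid days, as in SAP 4.4.1.

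- **Nobody now included is lost,** because the full span is itself a qualifying period.
- **At least 90 valid days are guaranteed,** since 0.50 × 180 = 90.
- **Extra valid days cannot disqualify,** because a period that qualified still exists with at least as many valid days. The 170-in-180 patient stays in whatever happens later.

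**What it leaves.** It remains a density rule, not a count. A patient with 91 valid days at each end of a 365-day span and 183 days without one between them (91 + 183 + 91 = 365) still fails. So does a patient with a valid day every third day (122/364 = 33.5%). A patient with 179 valid days in 179 is also still excluded, by the span condition.

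**Simpler alternative.** Keep the 180-day span and require at least 90 valid days. This also keeps all current patients and cannot penalise extra data, but it drops the density condition and admits wear as sparse as 90/365 = 25%. It too excludes 179 in 179.

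Under either version, describe the set as at least 90 valid days over at least 6 months, and tabulate valid days per patient. The cost is an edit to two SAP sections, a short search over pairs of valid days in the derivation program, and one table.

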#### **4.1.3 Intention-to-treat Population (ITT)**

The Intention-To-Treat Population will consist of all enrolled patients who received the ePRO application and the fitness tracker.

All objectives will be evaluated both on the Evaluable population and on the ITT population. In case that the Evaluable population will consist of less the 50% (< 50%) of the ENR populations, only the primary endpoint and the secondary endpoint on the type of physical activity will be assessed on the Evaluable populations while all endpoints will be assessed on the ITT population.

#### **4.1.4 SWITCH - ITT Population (ITT)**

The SWITCH population will consist of all enrolled patients who received the ePRO application and the fitness tracker and who switch to any newly approved drug for haemophilia during the observational period.

Subjects who switch to any newly approved drug for haemophilia A are divided in two subgroups:

- Subjects who switch to a replacement therapy
- Subjects who switch to a non-replacement therapy

This population will be used for one of the exploratory objectives.

## **4.2 ANALYSIS OF STUDY CONDUCT**

### **4.2.1 Subject enrolment and disposition**

For describing the subject disposition, the following populations will be summarized:

- Subjects enrolled (overall).
- Subjects enrolled but who did not receive the ePRO and wearable device and reasons for no dispensation.
- Subjects in the Evaluable population.
- Subjects in the ITT population.

For the overall report, the percentage denominator will be the number of the subjects in the related population.

### **4.2.2 Protocol violations**

All the protocol violations will be discussed case by case before database lock with the clinical team during the DRM and described in the DRM Report.

Number of occurrences and of subjects with at least one major and minor protocol violations will be summarized.

Protocol violations will be also shown by start of any newly approved drug for haemophilia.

#### **4.2.3 Study discontinuations**

Number and proportion of study completers will be shown.

The distribution of the time from baseline to discontinuation will be summarized using time-to-event method. In this case, Kaplan-Meier estimates and plots will be provided with 95% confidence interval bounds calculated per Greenwood method. Subjects who have not prematurely discontinued the trial will be censored at study termination.

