6.5 SUBJECT, STUDY AND SITE DISCONTINUATION

6.5.1 Subject Withdrawal

Patients have the right at any time and for any reason to withdraw their consent that their data are collected and used for the study. Reasons for withdrawal from the study may include, but are not limited to, the following:

- Patient withdrawal of consent at any time;
- Any medical condition that the investigator determines may jeopardize the patient's safety
 if he/she continues in the study;

- Investigator determines it is in the best interest of the patient;
- Patient's inability or unwillingness to comply with protocol requirements or noncompliance despite appropriate education measures taken by the clinical site.
- Patient died.
- Patient lost to follow-up.

Patients may elect to withdraw from the physical activity monitoring but continue participation in the remainder of the study. If a patient decides to withdraw only from the physical activity monitoring prematurely, the patient will continue with the follow-up visits as per the study protocol. Every effort should be made to obtain information on subjects who withdraw from the study. The primary reason for withdrawal from the study should be documented on the appropriate CRF page. Subjects will not be followed for any reason after consent has been withdrawn. Patients who withdraw from this part of the study will not be replaced.

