### **Amendment 2.0: 15 July 2022:**

In section 2.2.1 the types of physical activities identified by the fitness tracker have been listed.

In Section 4.1.4, the definition of SWITCH population has been added along with the classification of subjects who switch to a replacement or non-replacement therapy.

In Section 4.2.3, the time to discontinuation will be analyzed even if less than 30% of subjects will discontinue the study in order to provide an estimate of the median follow-up time.

In Section 4.4.2, the following changes have been done:

- Treatment regimen for bleeding: number and proportion of bleeding with adherence to treatment regimen in the week preceding the bleeding will be shown.
- HRQoL measured using the EQ-5D-5L will be analyzed monthly instead of every 3 months, deriving the timepoint from the date in which the questionnaire is recorded in the ePRO.
- Annualized Bleeding Rate: Number and proportion of subjects with at least one bleeding will be also shown.
- The analysis to explore the relationship between bleedings and physical activity has been explained better.

In Section 4.4.4, the following changes have been done:

- the definition of subgroups accordingly to the start of any newly approved drug for haemophilia has been updated.
- the analysis by month to observe the impact of COVID-19 has been added.

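### The Kaplan-Meier analysis of time to discontinuation in SAP 4.2.3 cannot give the median follow-up time it was kept for

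*SAP*

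**What the plan says.** SAP 4.2.3 gives the number and proportion of completers and then a survival-type analysis: "The distribution of the time from baseline to discontinuation will be summarized using time-to-event method". The method is Kaplan-Meier: "Kaplan-Meier estimates and plots will be provided with 95% confidence interval bounds calculated per Greenwood method". The censoring rule reads: "Subjects who have not prematurely discontinued the trial will be censored at study termination". The section does not say whether study termination means the patient's own last date or the end of the whole study.

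The purpose is given in the SAP's amendment rationale. Under Amendment 2.0, time to discontinuation is to be analysed "even if less than 30% of subjects will discontinue the study in order to provide an estimate of the median follow-up time". Section 4.2.3 names no other summary of follow-up. Subject disposition (SAP 4.2.1) lists populations only. The annualized bleeding rate analysis (SAP 4.4.2) shows total person-years, not a median.

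On size, SAP 2.3.1 states: "Of the anticipated 150 patients, 107 (71.3%) were included in the study". Planned observation is 12 months. It is prolonged to at most 18 months for patients who start a newly approved drug between months 6 and 12 (SAP section 2, Table 1).

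**The concern.** Time to discontinuation and length of follow-up are different quantities. In the first, a patient who completes is censored. In the second, the completer's end date is the observation of interest. A Kaplan-Meier median from the first coding is the time by which half the patients would have dropped out. Where most patients stay, it does not exist.

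The amendment keeps the analysis for the low-dropout case, which is where this median is least likely to be reached. The report would then show either no median follow-up at all, or a median time to dropout that could be mislabelled as follow-up.

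**Working it through.** The documents state no median follow-up, number of discontinuations or number of switchers, so there is no plan figure to reproduce.

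**Inputs.** N = 107 (SAP 2.3.1). Discontinuation under 30% (Amendment 2.0 rationale). Standard observation of 12 months (SAP section 2). Event and censoring as in SAP 4.2.3.

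**1. Events in the case the amendment addresses.** 0.30 × 107 = 32.1, so under 30% means at most 32 discontinuations.

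**2. Curve at month 12.** If all 32 occur by month 12 and nobody is censored before then, S(12) = 1 - 32/107 = 75/107 = 0.701. The Greenwood standard error is √(0.701 × 0.299 / 107) = 0.044, giving a 95% interval of 0.614 to 0.788. Even the lower bound is above 0.5. Fewer events put the curve higher.

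**3. Events needed for a median by month 12.** 107/2 = 53.5, so at least 54 discontinuations (50.5%). The result would still be a median time to discontinuation.

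**4. After month 12, with censoring at each patient's own end date.** The risk set shrinks to patients in the extension plus any whose last visit ran late. One event among r at risk multiplies the curve by (1 - 1/r). To stay under 30% overall, take 31 events by month 12 and one later (32 in all). Then S(12) = 76/107 = 0.710, and after the late event:

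| r at risk | S after one event |
|---|---|
| 10 | 0.710 × 9/10 = 0.639 |
| 5 | 0.710 × 4/5 = 0.568 |
| 3 | 0.710 × 2/3 = 0.474 |

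One withdrawal can therefore create an apparent median only if three or fewer patients remain at risk. The documents do not give r.

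**5. Simulation over assumed ranges.** N = 107, 2,000 runs per scenario, constant hazard, censoring at the patient's own end date. Discontinuation by month 12 was set at 5%, 10%, 20% or 29%. Late switchers were 5% to 30% of patients, starting uniformly between months 6 and 12. These rates are assumptions.

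- The planned Kaplan-Meier median was not reached in 83% to 99.7% of runs. In the rest it was reached only after month 12.
- The median of observed follow-up averaged 12.0 months in every scenario.
- The reverse Kaplan-Meier median (planned end of observation as event, discontinuation as censoring) also averaged 12.0 months.

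**6. The other reading of study termination.** If it means the last patient's last visit (End of Study, SAP Appendices 1 and 2), completers stay in the risk set after their own observation has ended. The risk set remains large, and with at most 32 events the curve again stays well above 0.5. The analysis gives no median follow-up on either reading.

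**The case against.** The best defence is that 4.2.3 is a correct analysis of what its heading names. Discontinuation as the event with completers censored is the standard coding for retention. The follow-up aim appears only in the amendment rationale, and the usual result, a median not reached, would mislead few readers. This largely stands, and it is why the point is minor. But the rationale explains why the current rule exists. The point is not that log and text differ. It is that the rule cannot serve its stated purpose and no other section does.

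Three stronger readings are tempting, and the documents do not support them.

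- **The plan is blind to loss of tracker data.** Protocol 6.5.1 does allow it: "Patients may elect to withdraw from the physical activity monitoring but continue participation in the remainder of the study". Such a patient is not an event in 4.2.3. But that section concerns leaving the study. Tracker attrition is described by exposure (SAP 4.3.1), compliance (4.3.2 and 4.3.2.1) and the Evaluable definition of at least 180 days' exposure and 50% compliance (4.1.2). A time-to-tracker-stop curve would be a useful option, not a missing necessity.
- **After month 12 the curve rests on a handful of switchers alone.** No number of switchers is given. Visits may move by about a month or more (Protocol 6.4.1), so ordinary completers can remain at risk past month 12. If censoring is at the whole-study end, this reading fails altogether.
- **Patients who leave during the extension will be counted as non-completers.** SAP 4.2.3 does not define a completer for those patients. The fair comment is that it should.

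**Conclusion.** The point holds in a limited form. The discontinuation curve estimates retention and cannot supply the median follow-up time for which Amendment 2.0 retains it. With 107 patients and at most 32 discontinuations, the curve is at or above 0.701 at month 12 and the median is not reached by then. This assumes that all 107 enter the analysis and that nobody is censored before month 12. A completion visit held somewhat early would shrink the risk set and could lower the value a little. Any median reached later is a time to discontinuation. If censoring is at the patient's own end date, its stability depends on a risk set whose size the documents do not give.

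The consequence is confined to one descriptive figure. It would be wrong to infer that any primary or secondary estimate is affected, since none uses this curve.

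**What to change.** In SAP 4.2.3:

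1. Report follow-up as the median, quartiles and range of (end of study date - baseline date + 1), the individual duration already defined in SAP 2.2.1, or as a reverse Kaplan-Meier median. Because the design fixes 12 months for most patients, the median will sit near 12. The lower quartile and range will be more informative about early loss.
2. Keep the existing Kaplan-Meier curve, described as time to discontinuation only.
3. State that patients who do not discontinue are censored at their own date of completion. The introduction to SAP section 4 already uses the date of patient completion or withdrawal as a data bound.
4. Show numbers at risk under the curve, or end it at month 12 and present the post-switch extension separately. State how completers are defined for patients in the extension.
5. Optionally, add a summary of time to the last valid tracker day.

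The cost is a few lines of SAP text and one or two extra summaries from dates already held. No new data are needed and no other result changes.
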